9.3.4 Supportive Analysis: Random Intercept (RI) Longitudinal Model

The model is similar to the model described in Section 9.3.2, but here the random effect, Z, will include only one random component, namely the intercept. The correlation between measurements within a patient is due to the common random intercept. This implies that the overall covariance matrix of Y is a block diagonal with a compound symmetry structure within patients. A robust estimate of the covariance matrix will be computed using a sandwich estimator with the

EMPIRICAL option in the PROC MIXED statement. Note that this option does not allow for usage of the Kenward-Roger degrees of freedom. The analysis will be implemented using SAS PROC MIXED with the code and detailed description provided in Section 17.2. Evaluation of non-inferiority and superiority will be done in the same manner as for the RIRS model.

9.3.5 Supportive Analysis: eGFR Change from Baseline

As an additional supportive analysis, the MMRM with the change from Baseline in eGFR will be fit. In this model the response variable will be the change from Baseline in eGFR at each scheduled study visit where eGFR is measured. eGFR values that were mapped to a visit with missing eGFR (Section 9.1) will be included in the analysis.

The model will include the following covariates:

- Intercept
- Baseline eGFR value
- Visit (as a class variable)
- Treatment arm (PRX-102; agalsidase beta)
- Visit by treatment arm group interaction

The first choice for the within-patient correlations will be an unstructured covariance matrix. It is important to note that due to the large number of visits, this matrix will be of dimension close to 30×30 and the model may not converge. If the model does not converge, the model will be fitted assuming a heterogeneous Toeplitz structure, followed by a homogeneous Toeplitz structure and then a compound symmetry structure until a stable model is achieved. Only data at scheduled visits will be used for this analysis. The Kenward-Roger degrees of freedom approximation will be used in calculating the Least Squares Means (LSMEANS) for the difference in the change from Baseline at 1 year and at 2 years between the two treatment arms.

The pseudo-SAS code for this analysis can be found in Appendix A.2 (Section 17).

Non-inferiority will be declared if the lower bound of the 95% CI for the contrast between treatment arms at the 2-year visit (Week 104) is greater than or equal to -6.0 mL/min/1.73 m²/year.

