13. CHANGES IN PLANNED ANALYSIS

13.1 Changes from Protocol to Interim Analysis SAP

The statistical section of the protocol is short and was not meant to provide detailed information for the analysis. Some of the changes in the planned analysis of PB-102-F20 are due to knowledge and insights gained in the overall clinical program of PRX-102. The analysis of the primary endpoint and its associated sensitivity analyses were discussed and agreed by the FDA. The main changes in the analysis plan compared to protocol are as follows:

- 1. The following endpoints were added: Infusion Related Reaction (IRR), Fabry Clinical Events and Achievement of Fabry Kidney Disease Therapeutic Goals.
- 2. Analysis sets: the protocol defined that a patient who received at least one complete dose will be included in the ITT and the SAP changed this to also include at least one partial dose. The definition of the Per Protocol population was also slightly revised.
- 3. The primary analysis was discussed with the FDA after protocol was finalized, and the agreement is described in the SAP. In particular added clarity on the choice of mixed model used, method of estimation and covariance matrix. UPCR which is a stratification factor was added as a covariate which is in line with ICH-E9. The discussion with the FDA included sensitivity for missing data and for modeling assumptions, which is different from what was described in the protocol.
- 4. The protocol specified assessment of the linearity assumption via residual plots. This was changed and instead it will be assessed by the MMRM model on the change in eGFR which does not assume linearity. In case of disagreement, additional assessments will be performed post-hoc.
- 5. The approach for multiplicity control was changed from the protocol, and was discussed and agreed with the FDA.
- 6. The only shift table for laboratory value will be for ADA. No other shift tables will be performed as no other safety laboratory values are of special interest.
- 7. Evaluation of Acute Kidney Injury is based on AE reporting and clinical judgment of the investigator and not as described in the protocol.
- 8. The statistical section of the protocol stated that hypersensitivity will be analyzed as an AE of special interest. Since IRR is a wider analysis which was added (see item 1 in this list), the analysis of hypersensitivity will be part of the IRR evaluation.

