17.3 MMRM Model for Change from Baseline - Specifications

The efficacy analysis is based on a longitudinal mixed model for the change from Baseline in eGFR. The pseudo code presented in this section relates to the analysis described in Section 9.3.59.3.5 and may need adjustment at the time of analysis. In particular, we would confirm the ESTIMATE instructions by LSMEANS.

The dependent variable, Y, will be the change from Baseline in eGFR values at the different visits, denoted below by eGFR_CH. The fixed part of the model will include the following terms: treatment arm (denoted by TRT), visit (denoted by VISIT; class variable based on visits and will include only scheduled visits), and treatment arm by visit interaction (denoted by VISIT*TRT) and eGFR0 to represent the eGFR at Baseline. Only observations at scheduled visits or observations that were mapped to a scheduled visit (See Section 9.1) will be included in the analysis. The pseudo-code presented here was modified compared to the version submitted to FDA in Sep 2020 by adding the Ismeans statement.

```
proc mixed data = DATA1S method=reml alpha=0.05 covtest;
class SUBJID TRT VISIT;
model eGFR_CH = TRT VISIT VISIT * TRT eGFR0 / s ddfm = KR cl;
repeated VISIT / subject=SUBJID type = UN;
lsmeans VISIT * TRT /cl;
estimate "Change from Baseline" TRT 1 -1
VISIT*TRT 0 0 0 0 ... 1, 0, 0, ..0
0 0 0 0 ... -1, 0, 0, ..0 / cl;
run;
```

DATA1S denotes the data, only at scheduled visits, at the interim analysis. The interaction contrast will be set to -1 and 1 for the visit associated with 1 year of treatment (Week 52; Visit 27) and set to -1 and 1 at the visit associated with 2 years of treatment (Week 104; Visit 53).

Non-inferiority is assessed based on the lower bound of the confidence interval obtained from the estimate statement labelled "Change from baseline".

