This approach is different than usual approach, that was also in the SAP version submitted to the FDA in Sep 2020 in which monotone missingness is achieved using Markov Chain Monte Carlo (MCMC) approach, within PROC MI with imputations done within each treatment arm. When implementing this approach prior to unblinding using dummy randomization codes, the algorithm did not converge and the reason was the large number of visits that had to be included in the model relative to the sample size. Another approach to rectify this and still using the MCMC was by imputing the missing data in several windows of time to reduce the number of visits at each such time window, however, it involved some arbitrary decisions about choice of windows. Although the approach chosen is based on single imputation, thanks to the large number of planned eGFR assessments, the low number of missing eGFR per patient and the reasonable assumption that they are MAR, it is justifiable to impute missing eGFR from subject's own data instead of borrowing data from other subjects. In case of borderline results (i.e., lower confidence bound very near the non-inferiority and/or superiority limit), additional sensitivity analysis might be performed (e.g., imputing the intermediate missing values via random draws from the distribution as predicted by the per-subject linear regression).

For the interim analysis, most of the patients who had missing data that should be imputed to ensure monotonicity had 1 or 2 missing eGFR assessments. A small number of patients had 3 missing eGFR assessments. One subject that completed the study had 5 missing assessments, and one ongoing subject had 6 missing assessments. This approach will be

discussed, by the blinded team, prior to the final analysis and if there will be concerns about the appropriateness of this approach (e.g., too many missing assessments for a single patient), it will be re-considered.

c) Once the monotone structure is achieved, missing eGFR after early termination will be imputed using the monotone reg command. To reflect the MAR assumption, imputations will be carried out and adjusting to treatment arm. Imputations will be carried out for all patients who terminated early and imputation will be carried out up to Visit 53. The following pseudo-code will be used in this step:

```

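### The last two covariance fallbacks in the supportive eGFR MMRM assume equal variance at every visit and modestly understate the Week 104 standard error; its two-year margin also carries a per-year unit

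*SAP*

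**What the plan says.** SAP 9.3.5 models change from baseline in eGFR at each scheduled visit, with visit as a class variable and Kenward-Roger degrees of freedom. It starts with an unstructured covariance but warns that "this matrix will be of dimension close to 30×30 and the model may not converge". The fallbacks are heterogeneous Toeplitz, "followed by a homogeneous Toeplitz structure and then a compound symmetry structure until a stable model is achieved". The SAP does not define a stable model. The code in SAP 17.3 has no EMPIRICAL option, so the SEs are model-based under every structure.

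Non-inferiority is declared if the lower 95% bound for the contrast "at the 2-year visit (Week 104) is greater than or equal to -6.0", and the unit printed after that figure is per year.

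Three other places bear on this:

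- SAP 13.1 item 4 drops the protocol's residual plots for linearity: "instead it will be assessed by the MMRM model on the change in eGFR which does not assume linearity".
- SAP 9.3.4 (random-intercept model) notes that its structure is compound symmetry within patients and protects against misspecification: "A robust estimate of the covariance matrix will be computed using a sandwich estimator".
- SAP 17.3 describes the contrast in prose: "The interaction contrast will be set to -1 and 1 for the visit associated with 1 year of treatment", and likewise for two years.

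**The concern.** The SAP's own random-intercept random-slope model (9.3.2) allows patients to have different slopes. If they do, the variance of change from baseline rises with time. A common-variance structure averages early and late visits, so it gives too small a variance at the last visit, which is the visit that carries the non-inferiority rule. Kenward-Roger adjusts for small samples under the assumed covariance; it does not repair a wrong variance pattern.

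The fallback path is realistic. The unstructured matrix is very large for this trial. SAP 17.6 reports that a different method, MCMC imputation on the same visit schedule, had already failed: "the algorithm did not converge and the reason was the large number of visits".

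At stake is an interval that is too narrow in an analysis with its own non-inferiority rule, shown in the forest plot beside the primary result (SAP 9.3). It would agree with non-inferiority somewhat too easily. The unit error sits in the same decision rule.

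**Working it through.** **1. The plan's own figure.** Protocol 10.1 gives 80% power for 44 vs 22 patients, difference 1.1, SD 1.5, two-sided alpha 0.049. SE = 1.5 × √(1/44 + 1/22) = 0.392; 1.1/0.392 = 2.81; 2.81 − 1.97 = 0.84; power = 79.95% (78.7% with the noncentral t). The figure reproduces. It also shows what 1.5 is: the SD of the annualized slopes entering a two-sample t-test, naturally read as fitted slopes that include measurement noise. The documents give no SE for the MMRM, so the rest is derived.

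**2. Size of the unstructured matrix.** SAP 17.6 lists 29 post-baseline visits: 29 × 30/2 = 435 covariance parameters for 78 patients.

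**3. Splitting the slope SD.** Fitted-slope variance = τ² + σ²/Sxx, where τ is the true between-patient slope SD and σ the residual SD. The documents do not give σ; it is assumed. Visit v is placed at (v − 1) × 14/365.25 years. Over baseline plus the 29 visits, Sxx = 10.19.

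- σ = 3: τ² = 2.25 − 9/10.19 = 1.367, so τ = 1.17.
- σ = 4: τ² = 2.25 − 16/10.19 = 0.680, so τ = 0.82.
- σ = 5 or 6: noise alone gives a fitted-slope SD of 1.57 or 1.88, already above 1.5. These values do not fit the planning SD on this reading.

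**4. Week 104 variance against the pooled variance.** Var(change at t) = τ²t² + 2σ². Adjusting for baseline does not alter the rounded error rates. At Week 104, t = 1.993 and t² = 3.973; the mean of t² over the 29 visits is 1.361. With complete data, the compound-symmetry variance is the average over visits. SE ratio = √(pooled/true); one-sided error = 1 − Φ(1.96 × ratio).

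| σ (assumed) | τ | True variance, Week 104 | Pooled variance | SE ratio | One-sided error |
|---|---|---|---|---|---|
| 3 | 1.17 | 1.367 × 3.973 + 18 = 23.43 | 1.367 × 1.361 + 18 = 19.86 | 0.92 | 3.6% |
| 4 | 0.82 | 0.680 × 3.973 + 32 = 34.70 | 0.680 × 1.361 + 32 = 32.93 | 0.97 | 2.8% |

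**5. Sensitivity.** If 1.5 were the true between-patient slope SD, with σ = 3 the ratio would be 0.88 and the error 4.2%; homogeneous Toeplitz gives 0.89 in that setting. At Week 52 the compound-symmetry SE is about right or slightly too large (ratio 1.00 to 1.10 over all settings tried), so the defect belongs to the late visit.

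**6. Would a sandwich SE help?** Simulation: 1,000 runs per setting, 52 vs 26 patients, 6 dropouts, truth on the margin, compound symmetry fitted. Here the slope SD is the true between-patient SD, so these rows test the remedy and do not estimate the size of the problem.

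| Slope SD, σ | Empirical SD | Model SE | Sandwich SE | Error, model | Error, sandwich |
|---|---|---|---|---|---|
| 1.5, 3 | 1.29 | 1.12 | 1.24 | 4.1% | 2.8% |
| 1.5, 5 | 1.94 | 1.77 | 1.82 | 4.0% | 2.8% |
| 3.4, 3 | 1.97 | 1.41 | 1.92 | 7.4% | 2.7% |
| 3.4, 5 | 2.39 | 1.97 | 2.33 | 6.2% | 3.4% |

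Monte Carlo error is about 0.5 to 0.8 percentage points. The sandwich SE helps but still falls short of the empirical SD in every row.

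**7. Margin.** −3.0 per year × 2 years = −6.0 mL/min/1.73 m². The contrast is a two-year change, so the per-year unit is wrong.

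**8. Contrast in 17.3.** The code pairs TRT 1 −1 with an interaction coefficient of 1 for the first arm and −1 for the second at one visit. That is the treatment difference at that visit. Only the prose gives the reverse order.

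**The case against.** The strongest reply is that this is a remote branch of a supportive analysis. Heterogeneous Toeplitz, the first fallback, estimates a separate variance at each visit and does not have the defect; both it and unstructured must fail first. The primary analysis is the two-stage quantile regression (SAP 9.2), and SAP 7.6.2 makes no significance claims from supportive analyses. For the linearity role, what matters is the visit-by-visit mean profile, and a narrow Week 104 interval would not hide curvature. SAP 13.1 also provides for post-hoc assessment if the results disagree. All of this stands, and it limits the point to a minor one. It does not remove it, because 9.3.5 states its own non-inferiority rule and the repair is a matter of wording.

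Three stronger readings are tempting.

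- A reader might take the SD of 3.4 in Protocol 10.5 and infer an SE 14-27% too small, with error of 4.6-7.7% (residual SD 3 to 6). But 3.4 is a tolerance in the 12-month power statement. It is neither an expected value nor a 24-month between-patient slope SD.
- A reader might infer from the prose in 17.3 that the Week 104 contrast is wrong. The printed code is a valid single-visit difference, and the SAP says the ESTIMATE instructions will be checked against LSMEANS.
- A reader might take the unit literally and infer a margin of −12.0 over two years (2 × −6.0). The rule applies −6.0 directly to the two-year contrast, so this is a labelling error and not a looser margin.

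**Conclusion.** The point holds as a minor one. If unstructured and heterogeneous Toeplitz both fail, the remaining structures understate the Week 104 SE whenever slopes differ between patients. Under compound symmetry, the SE is about 8% too small at residual SD 3 and about 3% at residual SD 4, with one-sided error of 3.6% and 2.8% against 2.5%.

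These figures rest on reading 1.5 as a fitted-slope SD, on an assumed residual SD that the documents do not give, on linear patient trajectories, and on near-complete data. Larger between-patient slope variation makes the understatement larger. A reader might infer that the trial's primary non-inferiority conclusion is at risk; it is not, because the quantile regression does not use this covariance model.

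The per-year unit on the −6.0 margin is a plain error.

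**What to change.** - In SAP 9.3.5, replace homogeneous Toeplitz and compound symmetry with heterogeneous-variance structures, for example heterogeneous compound symmetry (CSH) or heterogeneous AR(1) (ARH(1)). This is the more direct repair and keeps Kenward-Roger.
- If a constant-variance structure is kept as a last resort, add EMPIRICAL for that case, as in 9.3.4, and name the degrees-of-freedom method. The cost is that Kenward-Roger is lost, the interval widens, and some small-sample bias remains with about 26 control patients.
- Define a stable model, and report which structure was used.
- Give the margin as −6.0 mL/min/1.73 m², deleting the per-year unit.
- In 17.3, align the sign order in the prose with the code. The code contrast needs no change.

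All of this is SAP wording and at most one or two program options. It needs no new data and leaves the primary analysis as it is.

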9.3.6 Supportive Analysis: Two-stage with Quantile Regression – Additional Quantiles

The two-stage with quantile regression will be repeated for the ITT and PP, where in the 2nd stage the 25th and 75th quantiles as well as their difference will be estimated instead of the median.

9.4 Sensitivity Analysis for Missing Data

Analyses described in this section will be performed on the ITT set.

The primary analysis (Section 9.2) and the sensitivity analysis (Section 9.3) assume that the data are Missing At Random (MAR). The Sponsor acknowledges that missing data are a potential source of bias when analyzing data from clinical trials, particularly if the proportion of missing

values is substantial. Yet, a low rate of early termination has occurred in this 2-year study. The rate of intermediate missing eGFR data is low as well (out of the 30 planned eGFR assessments during the study, including Baseline, a small percent is missing). In light of this, the impact of missing data on the results appears to be minimal and the assumption of MAR seems reasonable. The impact of missing data will be assessed in sensitivity analyses, as outlined below.

The Sponsor made an effort to minimize the potential impact of COVID-19, particularly on the collection of blood for serum creatinine evaluation. There was one case of early termination since the start of the pandemic for a reason not related to the pandemic, and at the time of interim analysis there was minimal impact on the intermediate serum creatinine collection (this will be assessed by the blinded team as part of the blinded data review meeting).

The number and percent of early terminations will be summarized by treatment arms including the reasons for withdrawal. Time to discontinuation by treatment will be presented using a Kaplan-Meier analysis. In addition, the number of AKI episodes that precluded eGFR calculations and the number of patients with these episodes will be summarized by treatment arm.

In addition, Multiple Imputation (MI) will be used to assess the impact of missing data, as described below.

MI under the MAR assumption will be conducted for patients who early terminated. Missing data will be imputed within each treatment arm. Details are provided in Appendix A.2 (Section 17.6).

9.5 Sensitivity Analysis for Elevated Serum Creatinine

The analysis described in this section will be conducted on the ITT set.

AKI Episodes are reported by the investigators as an AE and eGFR measurements during the time of the AE will be excluded from the analysis (see Section 9.1).

As a sensitivity analysis to the primary analysis, in addition to the excluded eGFR values during an AKI episode, any eGFR value associated with events of an elevated serum creatinine, as described in the study protocol, will be excluded from the analysis as well. An elevated serum creatinine is defined by a 1.5-fold increase or greater compared to the immediate previous serum creatinine value as long as that measurement was taken no more than 34 days before (visits are every two weeks, so this allows for a situation that previous visit is missing and 6 days to account for allowed window for the visits).

The number of such observations and the number of patients with at least one such an observation will be summarized by treatment arm.

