8.3.2.3 Acute Kidney Injury

Episodes of Acute Kidney Injury (AKI) will be considered adverse events. AKI will be defined by a 1.5 fold or greater increase in serum creatinine from the immediately previous laboratory value and assessment by the investigator. The Protalix Medical Director will work with the investigator to ensure that such changes in renal function are thoroughly evaluated. See Section 10.6 Missing Data for further description of how episodes of AKI will be handled in data analysis for efficacy.

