9.2.4 All Odd Numbered Visits (3 through 53)

Serum creatinine and cystatin C (pre-infusion)

9.2.5 Visits 2, 15, 28, and 2 weeks after Visit 53 (± 3 Days)

Plasma samples for PK analysis for 30 enrolled subjects, last sample at 14 ± 3 days post infusion

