16.2 Study Milestones

Seventy-eight (78) patients were randomized into the study. The Last Patient Last Visit (LPLV) for the interim analysis was in October 2020 and for final analysis was in October 2021. The Data Base Lock (DBL) and unblinding for the interim analysis was in April 2021, and the DBL for final analysis is anticipated in the first quarter of 2022 (Table 4).

Tentative Timelines

Enrollment Complete LPLV Date DBL

Interim Analysis September 2019 October 2020 April 2021

Final Analysis N/A October 2021 Q1 2022

Table 4: BALANCE Interim and Final Analyses - Key Milestones

Out of the 78 patients randomized to the study, 6 (7.7%) patients have discontinued during the study. Data collection was completed for the majority of the patients (61%) at the time of the LPLV for the interim analysis. Table 5 presents the key milestones:

Table 5: Predicted Number of Patients per Milestone

	Interim Analysis	
	LPLV	DBL and Unblinding
Date	Oct 2020	Apr 2021
Number of patients completed 24 months of treatment or early termination	48 (61%)	60 (77)
Number of patients completed between 18-23 months of treatment	13 (17%)	13 (17%)
Number of patients completed between 12- 17 months of treatment	17 (22%)	5 (6%)
Total	78	78

Figure 1 provides a schematic of the study with key milestones and timelines for the development programs in the EU and the US, and points out the 9-12-month period (April 2021 to Q1 2022) between the two DBL, with a 6-month period between the DBL for the interim analysis and the LPLV for the final analysis.

Figure 1: Schematic of BALANCE Development Program and Study Timelines

	EU Development milestones			US Development milestones			
Oct 20, LPLV		Apr 21, DBL for		Oct 21, LPLV Final MAA	Q1 22, DBL for Final		BLA
for IA		IA					
Q4 20	Q1 21	Q2 21	Q3 21	Q4 21	Q1 22	Q2 22	Q3 22

The primary endpoint of eGFR slope is derived from serum creatinine measurements. Serum creatinine is assessed on a monthly basis, so at the time of LPLV for the interim analysis, at least 90% of the blood samples were completed and available. At the time of DBL for the interim analysis and unblinding about 96% of blood samples were taken.

The implication of these milestones is that the risk of bias for the final analysis is low and the creation of firewalls and other measures will further reduce this risk.

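### The 34-day look-back in the elevated-creatinine sensitivity analysis is built on the two-weekly infusion calendar, so it does not allow for a missed four-weekly creatinine sample as intended (minor)

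*SAP*

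**What the plan says.** SAP 9.5 plans a sensitivity analysis to the primary slope analysis. Beyond the values already removed during reported AKI episodes, "any eGFR value associated with events of an elevated serum creatinine, as described in the study protocol, will be excluded from the analysis as well". The trigger is numerical: "An elevated serum creatinine is defined by a 1.5-fold increase or greater compared to the immediate previous serum creatinine value", but only "as long as that measurement was taken no more than 34 days before". The reason given for 34 days is that "visits are every two weeks, so this allows for a situation that previous visit is missing and 6 days to account for allowed window".

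The sampling calendar is set elsewhere. Protocol 9.2.4 and the flow chart in Protocol 9.1 place serum creatinine at the odd-numbered visits. Biochemistry, which includes creatinine (Protocol 8.3.1), adds samples at visits 14, 20 and 40. SAP 16.2 says the same in general terms: "Serum creatinine is assessed on a monthly basis". The imputation code in SAP 17.6 lists the resulting 30 eGFR time points.

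The protocol definition that SAP 9.5 points to (Protocol 8.3.2.3) is a "1.5 fold or greater increase in serum creatinine from the immediately previous laboratory value", together with the investigator's assessment. It sets no limit on how old the previous value may be.

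**The concern.** The rationale treats the visit interval as if it were the creatinine interval. Infusion visits are two weeks apart, but planned creatinine samples are mostly four weeks apart. A look-back meant to survive one missed sample therefore has to be built on 28 days, not 14.

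At stake is whether this analysis does what it says. It is meant to show how the primary result changes when creatinine surges that were not reported as AKI are removed. If a sample is missed just before a surge, the first value after the gap cannot be tested, and an eGFR value that the section intends to remove stays in that patient's slope.

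**Working it through.** **Inputs**
- Infusion visits every 14 days (Protocol synopsis).
- Visit window ±3 days (Protocol 9.2.3; SAP 6), so the gap between two visits can vary by ±6 days.
- Creatinine at the 27 odd visits from 1 to 53, plus visits 14, 20 and 40: 27 + 3 = 30, matching the count in SAP 9.4 and the list in SAP 17.6.
- Look-back limit 34 days (SAP 9.5).

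**1. The plan's own figure.** One missed two-weekly visit plus windows: 2 x 14 + 2 x 3 = 34 days. The figure reproduces from its stated rationale.

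**2. Complete sampling.** Dating visit v at day 14 x (v - 1), the 30 samples give 29 gaps: 23 of 28 days and 6 of 14 days. The longest, with windows, is 28 + 6 = 34 days. So 34 days just covers every consecutive pair when nothing is missed.

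**3. One missed sample.** Remove each of the 28 interior samples in turn (30 less the first and last) and take the gap between its neighbours:

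| Missed sample | Cases | Gap (days) | With ±6 days | Next value testable at 34? | At 62? |
|---|---|---|---|---|---|
| V14, V20 or V40 | 3 | 28 | 22–34 | yes | yes |
| V13, V15, V19, V21, V39 or V41 | 6 | 42 | 36–48 | no | yes |
| any other interior odd visit | 19 | 56 | 50–62 | no | yes |

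In 6 + 19 = 25 of 28 cases (89%) the next value is out of reach even at the most favourable window, since 42 - 6 = 36 > 34. A sample deferred to the next two-weekly visit has the same problem: 28 + 14 = 42 days, or 36 to 48 with windows.

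**4. Look-back that meets the stated intent.** One missed four-weekly sample plus windows: 2 x 28 + 6 = 62 days. All 28 of 28 single-miss cases then stay testable, against 3 of 28 at 34 days. Two consecutive missed odd visits on the plain four-weekly grid would leave 3 x 28 = 84 days and remain outside, but the stated intent covers only one miss.

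**The case against.** The best defence is that 34 days is workable for the planned schedule and only its explanation is wrong. With complete sampling every consecutive pair is covered (step 2). After a miss, only the first value that follows goes untested, and an unscheduled sample could shorten the gap. Reported AKI is already excluded from start to end of the adverse event (SAP 9.1), and clinically significant laboratory abnormalities must be reported as adverse events (Protocol 8.3.2.1), so the exposed values are few. SAP 9.4 describes intermediate missing eGFR as low, and SAP 17.6 reports that at the interim most affected patients had one or two missing assessments. The SAP also governs where it differs from the protocol on planned analyses (SAP 1), so the absence of a time limit in the protocol is not itself an error. All of this stands, and it sets the severity. It does not rescue the stated allowance for a missing visit, which the number does not deliver.

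A reader might also infer that the rule removes only the first raised value of an episode and keeps the rest. The text does not settle this. The exclusion covers values associated with an event, which can include later ones. On the other hand, the trigger compares each value only with the one just before, and the summary counts single observations: "The number of such observations and the number of patients with at least one such an observation will be summarized by treatment arm". No end of an event is defined. That calls for clarification and is not a demonstrated error.

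**Conclusion.** The look-back is wrong as written: it fails its own stated purpose in 25 of 28 single-miss cases. This rests on the planned schedule, windows of ±3 days, one missed sample at a time and no unscheduled sample in the gap.

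Severity is minor. A reader might go further and conclude that surges are missed after any gap, or that a reassuring sensitivity result would be an artefact that endangers the non-inferiority conclusion. The documents do not support either. Missing visit 14, 20 or 40 leaves the rule working, and testing resumes once the next pair of samples is close enough. Nor can one patient's slope shift be set against the 3.0 mL/min/1.73 m²/year margin, which applies to a between-arm difference in median slopes (SAP 9.2). The effect on that difference depends on how many unreported rises directly follow a missed sample. The documents do not give that number; the effect is probably small.

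**What to change.** In SAP 9.5, before database lock, change the look-back from 34 to 62 days. Reword the parenthesis to say that serum creatinine is planned every four weeks, so that 2 x 28 days allows for one missed sample and 6 days for the visit windows.

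The cost is one sentence and one constant in the program. The downside is that a few more values may be excluded in this one sensitivity analysis. Some of them may reflect slower true decline over the longer gap rather than a transient surge, and the report should say so.

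As a clarification only, state whether later raised values in the same episode count as associated with the event and, if so, how the episode ends. That choice needs care: a rule that runs until creatinine falls back below a threshold would remove every later value of a patient whose rise never recovers, and with it true progression.
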